- c. Cord blood must be obtained on the day of birth. Cord blood is collected from the umbilical cord vein attached to the placenta after the umbilical cord has been clamped and cut. If cord blood is unavailable, a venous blood sample may be collected from the infant participant up to 24 hours after birth. The infant's weight must be used to determine the volume of blood that can be collected.
- d. The time period for actively eliciting and collecting AEs and SAEs ("active collection period") begins at birth and continues through and including a minimum of 28 days after birth. From Visit 2 until the last study visit, only AEs of special interest, MAEs, and SAEs, including hospitalizations, will be reported.

CCI

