3.2. Infant Participant

Primary Objective Infant Participant	Estimands	Primary Endpoints Infant Participant
To assess the safety of maternal immunization in infants born to women ≥ 18 through 49 years of age who were vaccinated with 1 dose of RSV vaccine during pregnancy	In infant participants born to the maternal participants receiving 1 dose of investigational product: 
• The percentage of infant participants with specific birth outcomes• The percentage of infant participants having AEs• The percentage of infant participants having SAEs, AEs of special interest (congenital anomalies, developmental delay), and MAEs	
• Specific birth outcomes• AEs from birth to 1 month of age• SAEs, AEs of special interest (congenital anomalies, developmental delay), and MAEs through 12 months of age• Congenital anomalies (defined as structural or functional anomalies [eg, metabolic disorders] that occur during intrauterine life and can be identified prenatally, at birth or later in life²⁶)

Secondary Objective Infant Participant	Estimands	Secondary Endpoints Infant Participant

To describe RSV antibody levels in infants born to women ≥ 18 through ≤ 49 years of age who were vaccinated with 1 dose of RSV vaccine during pregnancy
	
In infant participants born to maternal participants receiving 1 dose of investigational product and in compliance with the key protocol criteria (evaluable participants):
 
 • Functional antibody levels estimated by the GMT for RSV A– and RSV–B neutralizing antibody titers • GMR, estimated by the ratio of the GMTs for RSV A– and RSV–B neutralizing antibody titers of the RSV vaccine group and the placebo group 	
 • RSV A– and RSV B–neutralizing antibody titers measured at: 
 • birth • 1 month • 2 months • 4 months • 6 months 
Note: Infant participants will be randomly assigned to 1 of 2 blood sampling schedules.

CCI

CCI

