8.3.1. Time Period and Frequency for Collecting AE and SAE Information

The time period for actively eliciting and collecting AEs and SAEs (“active collection period”) for each maternal participant including her fetus begins from the time the maternal participant provides informed consent, which is obtained before participation in the study (ie, before undergoing any study-related procedure and/or receiving investigational product), through and including a minimum of 1 month after the last administration of the investigational product.

In this study, the investigator and site staff will ensure the active elicitation and collection of AEs and SAEs through 1 month after vaccination. From 1 month after vaccination until the maternal participant completes the study, MAEs and SAEs will be collected.

For the infant participant, the time period for actively eliciting and collecting AEs and SAEs (“active collection period”) begins at birth and continues through and including a minimum

of 28 days after birth. From Visit 2 until the last study visit, only AEs of special interest, MAEs, and SAEs, including hospitalizations, will be reported.

CCI

In addition, AEs occurring up to 48 hours after blood draws CCI that are related to study procedures must be reported in the CRF.

For maternal participants who are screen failures, the active collection period ends when screen failure status is determined.

If the participant withdraws from the study and also withdraws consent for the collection of future information, the active collection period ends when consent is withdrawn.

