- The investigator or an authorized designee completes the CRF.

8.10.2.2. Infant Participants: Visit 2 – 1-Month Follow-up (28 to 35 Days After Birth)

- Measure vital signs, including rectal temperature, heart rate, and respiratory rate.
- Obtain and record infant's length, head circumference, and weight.
- Obtain and record background factors as described in [Section 10.5](#).
- Perform physical examination, if not performed as part of routine care, evaluating any clinically significant abnormalities within the following body systems: general appearance; skin; head, eyes, ears, nose, and throat; heart; lungs; abdomen; back; musculoskeletal; extremities; genitourinary; neurological; and lymph nodes. Newly identified abnormal findings must be recorded on source documents and the physical examination page and, if considered clinically significant in the judgment of the investigator/examiner, on the AE page of the CRF.
 - Obtain and record details of any newly emergent congenital medical history.
- Obtain and record details of any vaccinations, monoclonal antibodies (eg, Synagis), or blood transfusions (eg, whole blood, packed cells) given since the last visit.
- For infants randomly assigned to the Visit 2 (1-month follow-up) and Visit 4 (4-month follow-up) sampling schedule, collect a blood sample of up to 5.0 mL for serologic assessments based on the infant's weight (refer to [Table 5](#)).
- Record any medication as described in [Section 6.5.5](#). Record AEs as described in [Section 8.3](#) and [Section 10.3.3](#).

- Ask the parent(s)/legal guardian(s) to contact the investigator immediately if any significant illness or hospitalization occurs or if the infant meets the acute illness visit criteria.
- Complete the infant participant's source documents.
- The investigator or an authorized designee completes the CRF.

8.10.2.3. Infant Participants: Visit 3 – 2-Month Follow-up (49 to 63 Days After Birth)

- Measure vital signs, including rectal temperature, heart rate, and respiratory rate.
- Obtain and record the infant's length, head circumference, and weight.
- Obtain and record background factors as described in [Section 10.5](#).

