- Perform physical examination, if not performed as part of routine care, evaluating any clinically significant abnormalities within the following body systems: general appearance; skin; head, eyes, ears, nose, and throat; heart; lungs; abdomen; back; musculoskeletal; extremities; genitourinary; neurological; and lymph nodes. Newly identified abnormal findings must be recorded on source documents and the physical examination page and, if considered clinically significant in the judgment of the investigator/examiner, on the AE page of the CRF.
 - Obtain and record details of any newly emergent congenital medical history.
- Obtain and record details of any vaccinations, monoclonal antibodies (eg, Synagis), or blood transfusions (eg, whole blood, packed cells) given since the last visit.
- For infants randomly assigned to the Visit 3 (2-month follow-up) and Visit 5 (6-month follow-up) sampling schedule, collect a blood sample of up to 5.0 mL for serologic assessments based on the infant's weight (refer to [Table 5](#)).
- Record any medication as described in [Section 6.5.5](#).
- Record AEs as described in [Section 8.3](#) and [Section 10.3.3](#).
- Ask the parent(s)/legal guardian(s) to contact the investigator immediately if any significant illness or hospitalization occurs or if the infant meets the acute illness visit criteria.
- Complete the infant participant's source documents.
- The investigator or an authorized designee completes the CRF.

8.10.2.4. Infant Participants: Visit 4 – 4-Month Follow-up (112 to 126 Days After Birth)

- Measure vital signs, including rectal temperature, heart rate, and respiratory rate.
- Obtain and record the infant’s length, head circumference, and weight.
- Obtain and record background factors as described in [Section 10.5](#).
- Perform physical examination, if not performed as part of routine care, evaluating any clinically significant abnormalities within the following body systems: general appearance; skin; head, eyes, ears, nose, and throat; heart; lungs; abdomen; back; musculoskeletal; extremities; genitourinary; neurological; and lymph nodes. Newly identified abnormal findings must be recorded on source documents and the physical examination page and, if considered clinically significant in the judgment of the investigator/examiner, on the AE page of the CRF.
 - Obtain and record details of any newly emergent congenital medical history.

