10.3.1.1. Definition of MAE

An MAE is defined as a nonserious AE that results in an evaluation at a medical facility.

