3.5. Safety Endpoints

3.5.1. Adverse Events

AEs will be captured and reported in accordance with Pfizer reporting standards.

For maternal participants the time period for actively eliciting and collecting AEs and SAEs (“active collection period”) begins from the time the maternal participant provides informed consent, which is obtained before participation in the study (ie, before undergoing any study-related procedure and/or receiving investigational product), through and including a minimum of 1 month (30 days) after the last administration of the investigational product. In this study, the investigator and site staff will ensure the active elicitation and collection of AEs and SAEs through 1 month after vaccination. From 1 month after vaccination until the maternal participant completes the study, MAEs and SAEs will be collected.

For infant participants, the time period for actively eliciting and collecting AEs and SAEs (“active collection period”) begins at birth and continues through and including a minimum

of 28 days after birth. From Visit 2 until the last study visit, only AEs of special interest, MAEs, and SAEs, including hospitalizations, will be reported.

For maternal participants who are screen failures, the active collection period ends when screen failure status is determined. If the participant withdraws from the study and also withdraws consent for the collection of future information, the active collection period ends when consent is withdrawn.

During the active collection period, both nonserious AEs and SAEs are recorded on the case report form (CRF) and will be categorized according to the current version (at the time of reporting) of the Medical Dictionary for Regulatory Activities (MedDRA).

An immediate AE is defined as any AE that occurred within the first 30 minutes after administration of the investigational product for maternal participants.

An MAE is defined as a nonserious AE that results in an evaluation at a medical facility. From Visit 2 (for infant participants) or from 1 month after vaccination (for maternal participants) until the participant completes the study, MAEs and SAEs will be collected.

AEs of special interest for infant participants are major congenital anomalies and developmental delays and are collected from birth through the end of the study (12-month-of-age visit).

CCI

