6.1.2.2. AEs Within 1 Month of Age

- Analysis set: Safety (Section 4).
- Analysis methodology: Descriptive summary statistics for Tier 3 events; difference and 95% CI between the vaccine group and the placebo group for Tier 2 events.
- Intercurrent events and missing data: For participants who discontinue, all collected data will be included; missing AE dates will be imputed as described in Pfizer's Vaccine Statistics Rulebook.
- For each group, number of participants with AEs **CCI** within 1 month (30 days) (n), %, and 95% CI will be presented for any AE, each SOC, and each PT within each SOC, by vaccine group. For AEs classified as Tier 2 events, difference in proportions and associated 2-sided 95% CI between the vaccine group and the placebo group will be presented.

6.1.2.3. AEs of Special Interest (Major Congenital Anomalies, Developmental Delays), MAEs, and SAEs Through 12 Months of Age

- Analysis set: Safety (Section 4).
- Analysis methodology: Descriptive summary statistics.
- Intercurrent events and missing data: For participants who discontinue, all collected data will be included; missing AE dates will be imputed as described in Pfizer's Vaccine Statistics Rulebook.
- For each group, number of participants with AEs of special interest, MAEs, and SAEs through 12 months of age (n), %, and 95% CI will be presented for any event, each SOC, and each PT within each SOC, by vaccine group. For AEs of special interest, difference in proportions and associated 2-sided 95% CI between the vaccine group and the placebo group will be presented.

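### The SAP counts infant AEs to 30 days, but some are guaranteed collection only to day 28, and the Visit 3 to 6 instructions conflict with the limit on later AE reporting

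*Protocol*

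**What the plan says.** **Collection.** For infants, the active collection period "begins at birth and continues through and including a minimum of 28 days after birth" (Protocol 1.3.2, footnote d; also Protocol 8.3.1 and SAP 3.5.1). After that, "From Visit 2 until the last study visit, only AEs of special interest, MAEs, and SAEs, including hospitalizations, will be reported" (Protocol 8.3.1, repeated in SAP 3.5.1). Visit 2 has a window of 28 to 35 days after birth (Protocol 1.3.2 and 8.10.2.2).

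**Counting.** The primary infant endpoint in Protocol 3.2 is "AEs from birth to 1 month of age". SAP 6.1.2.2 makes this 30 days: the number of infants with AEs "within 1 month (30 days) (n), %, and 95% CI will be presented for any AE". SAP 3.5.1 also uses 30 days for Tier 2: a preferred term qualifies when at least four participants in a group report it in that time.

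**Examination findings after Visit 2.** Protocol 8.10.2.3 to 8.10.2.6 (Visits 3 to 6) require a new abnormal finding to be recorded, "if considered clinically significant in the judgment of the investigator/examiner, on the AE page of the CRF". The same lists tell sites to record AEs under Sections 8.3 and 10.3.3. The medically attended event is defined in Protocol 10.3.1.1: "An MAE is defined as a nonserious AE that results in an evaluation at a medical facility".

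**The concern.** Two sets of instructions do not fit together.

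First, the counting window for a primary infant endpoint is longer than the collection guaranteed for every infant. Take a mild rash on day 29 that nobody takes to a clinic. If Visit 2 was on day 28, the rash is not reportable, and the infant is counted as free of that event through day 30. If Visit 2 was on day 33, the same rash is reportable and counted. The percentage then depends partly on appointment dates. The maternal rule has no such gap: SAP 3.5.1 sets maternal collection at a minimum of 30 days, which matches the 30-day count in SAP 6.1.1.3.

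Second, after Visit 2 a site has two instructions for a nonserious finding first noticed at a study examination. One sends it to the AE page if it is clinically significant. The other limits reporting to AEs of special interest (AESIs), MAEs and SAEs. Two sites can each follow the protocol and produce different records. The MAE definition does not say whether a scheduled study visit can count as the evaluation, and infant MAEs through 12 months are also a primary endpoint.

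The analysis is descriptive throughout (SAP 5.1), so the percentages are themselves the result. Each needs one window and one recording rule.

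**Working it through.** **The plan's own figure.** The documents give no figure for this point. Their only event-probability calculation, Table 6 in Protocol 9.2, reproduces: 1 − (1 − 0.01)^100 = 0.634, against 63% stated. It is not in dispute.

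**Step 1: the gap.** Inputs are collection of all AEs until Visit 2, a Visit 2 window of days 28 to 35, and a count to day 30. Uncollected counted days: g = max(0, 30 − Visit 2 day).

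| Visit 2, days after birth | 28 | 29 | 30 to 35 |
|---|---|---|---|
| g (days) | 2 | 1 | 0 |
| share of 30 days | 6.7% | 3.3% | 0% |

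If Visit 2 is spread evenly over its eight days (an assumption), the mean gap is 3/8 = 0.375 day, or 1.25% of the window.

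The gap also depends on how the rules are read. If events on the day of Visit 2 are already restricted, g is 3, 2 and 1 for visits on days 28, 29 and 30. If the 30 days are Days 1 to 30 with birth as Day 1 (SAP 3.4.2), the count ends 29 days after birth, and a day-28 visit leaves one day.

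**Step 2: effect on the percentage.** Assume a constant hazard and that every AE is of the kind no longer collected. The second assumption overstates the loss. For a true 30-day risk p, the observed risk is 1 − (1 − p)^((30 − g)/30).

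| True p | Observed, all visits day 28 | Loss (points) | Loss, even spread (points) |
|---|---|---|---|
| 30% | 28.3% | 1.7 | 0.3 |
| 40% | 37.9% | 2.1 | 0.4 |
| 50% | 47.6% | 2.4 | 0.4 |
| 60% | 57.5% | 2.5 | 0.5 |

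The even-spread loss is the sum of the losses at g = 2 and g = 1, divided by 8. At 30% that is (1.68 + 0.84)/8 = 0.32. At 60% it is (2.52 + 1.24)/8 = 0.47. The documents give no infant AE rate, so p is an assumed range. On the stricter reading, where events on the visit day are also lost, the worst case is 2.5 points at 30% and 3.6 at 50%.

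**Step 3: scale.** With 650/5 = 130 per group, an approximate 95% CI half-width at 40% is 1.96 × √(0.4 × 0.6/130) = 8.4 points. The even-spread loss at 40% is about 0.0039 × 130 = 0.5 infant per group, and the worst case is 2.7 infants.

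**Step 4: Tier 2 status.** For a preferred term with a true 30-day rate of 3% and N = 130, the binomial probability of four or more infants is 0.549. With all visits on day 28 it falls to 0.496.

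**Step 5: comparison between arms.** Assessing staff are blinded (Protocol 6.3.1), so Visit 2 timing should not differ by arm. A loss shared by all groups barely moves a difference: 50% v 40% becomes 47.6% v 37.9% in the worst case, or 9.7 points instead of 10.

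**Step 6: the later visits, side by side.**
- 8.10.2.3 to 8.10.2.6: clinical significance alone sends a new finding to the AE page.
- 8.3, cited in the same lists: after Visit 2, only AESIs, MAEs and SAEs, plus procedure-related AEs within 48 hours of a blood draw.
- 10.3.3, also cited there: its table has all nonserious AEs recorded on the CRF.

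The visible text gives no order of precedence. Visit 3 opens at day 49, so these findings reach the 30-day table only if onset is dated back to the first month. No rate of examination findings is given, so any effect on MAE percentages cannot be computed.

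**The case against.** The strongest reply is that these are wording mismatches with little consequence, and much of it stands.

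- A reader might infer that all nonserious infant collection stops at Visit 2. It does not. MAEs are nonserious by definition and continue to 12 months, as do AESIs; procedure-related AEs around blood draws are also reportable. Only the remainder is lost.
- A reader might infer that study-visit findings will be labelled MAEs and dilute the vaccine-placebo difference. The documents do not support this. The definition requires the AE to lead to the evaluation, which a scheduled visit is not. No rate of such labelling is given. SAP 6.1.2.3 plans only n, % and CI by group for infant MAEs, with a difference for AESIs alone. The SAP limits Tier 2 to 30 days, before Visit 3 opens.
- The examination instruction has a purpose: congenital anomalies identified later and developmental delay are AESIs. The pointer to 8.3 also brings in the reporting limit.
- The 28 days are a minimum, and many infants will be seen on day 30 or later.
- Text next to the rule in 8.3.1 and within the infant AE endpoint is blacked out, so the full rule is not visible.

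Two things remain. The minimum does not help an infant seen on day 28 or 29, because the restriction starts at Visit 2. And a pointer to 8.3 beside an unrestricted instruction and a pointer to 10.3.3 does not tell a site which to follow.

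**Conclusion.** The concern holds in a limited form. The SAP counts infant AEs, and assigns Tier 2 status, over a period longer than the one in which every infant is under full collection. Affected are nonserious AEs that are not medically attended, not AESIs and not procedure-related, in infants whose Visit 2 falls on day 28 or 29.

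The understatement of the absolute percentage is about 0.3 to 0.5 points with evenly spread visits, and at most 1.7 to 2.5 points with every visit on day 28. These figures rest on a constant hazard, an assumed 30-day risk of 30 to 60%, and collection through the day of Visit 2. They are small against a CI half-width of about 8 points, and no bias between arms is expected. Tier 2 status of a borderline term can change.

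The conflict over examination findings at Visits 3 to 6 is also real. It makes recording depend on the site, but its effect on the descriptive infant MAE percentages is unknown. It should not be presented as a bias toward no difference.

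**What to change.** 1. **SAP 6.1.2.2, and the infant Tier 2 rule in SAP 3.5.1:** count infant AEs from birth through 28 days after birth, and state how days are numbered. Cost: a few events collected on days 29 and 30 leave the table, and the Tier 2 window becomes 28 days for infants and 30 for mothers. The alternative is to collect all infant AEs to day 30 whatever the Visit 2 date. That keeps the 30-day window but adds collection for infants seen early; the weekly parent contacts in Protocol 1.3.2 could carry it.
2. **Protocol 8.10.2.3 to 8.10.2.6:** reconcile with 8.3.1, so that a finding after Visit 2 goes to the AE page only if it is an AESI, MAE, SAE or reportable procedure-related AE. Other findings stay on the physical examination page. Make the reference to 10.3.3 subject to the same limit.
3. **Protocol 10.3.1.1:** state that a scheduled study visit is not by itself the evaluation that makes an event an MAE.

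Items 2 and 3 are wording changes and need no new data.

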8.3.1.1. Reporting SAEs to Pfizer Safety

All SAEs occurring in a participant during the active collection period are reported to Pfizer Safety on the CT SAE Report Form and the Exposure During Pregnancy Supplemental Form if applicable.

If the outcome of the pregnancy meets the criteria for an SAE (ie, ectopic pregnancy, spontaneous abortion, including miscarriage and missed abortion, intrauterine fetal demise, neonatal death defined as those that occur within 1 month of birth, or congenital anomaly in a live-born baby, a terminated fetus, an intrauterine fetal demise, or a neonatal death), the investigator should follow the procedures for reporting SAEs. In addition, infant deaths after 1 month of age should be reported as SAEs.

Further follow-up may be requested by the sponsor and will be handled on a case-by-case basis (eg, follow-up on preterm infants to identify developmental delays).

SAEs occurring in a participant after the active collection period has ended are reported to Pfizer Safety if the investigator becomes aware of them; at a minimum, all SAEs that the investigator believes have at least a reasonable possibility of being related to investigational product must be reported to Pfizer Safety.

The same is applied for those SAEs after the active collection period has ended should they occur to the fetus. In addition, infant deaths that occur after 12 month of age should be reported as SAEs when the investigator believes the death has at least a reasonable possibility of being related to investigational product.

Follow-up by the investigator continues throughout and after the active collection period and until the event or its sequelae resolve or stabilize at a level acceptable to the investigator, and Pfizer concurs with that assessment.

